10.23.3 Time to First Onset of AE

The time to first onset of AE (expressed in days) will be defined as:

(AE start date – IMP Start Date) + 1

Based on the above value time to first onset of TEAE (as defined in Section 12.8.1.2) will be categorized as:

- 1 to 7 days
- 8 to 14 days
- 15 to 28 days
- 29 to 42 days
- 43 to 84 days
- > 84 days.

If onset time is shorter than 1 day, it will be included in the 1-7 days category.

10.23.4 AE Duration

The AE duration (expressed in days) will be defined as:

(AE stop date – AE start date) + 1

The duration will not be derived in case of partial or missing start or stop date.

Based on the above value the AE duration will also be categorized as follows:

- 1 to 7 days
- 8 to 14 days
- 15 to 28 days
- 29 to 42 days
- 43 to 84 days
- > 84 days
- Ongoing,
- Indeterminate.

If AE stop date is missing and the outcome of the AE is "Not recovered, Not resolved", the AE will be categorized as "Ongoing".

If the AE start date is partial or missing and the AE is not considered as "Ongoing", the AE will be classified as "Indeterminate".

10.24 Laboratory Data

10.24.1 Strip-sign Handling

In cases a hematology or chemistry value has been recorded as '>x', ' \ge x', ' \ge x', ' \le x' or '<x', the value will be imputed as "x" to perform summary statistics but the strip sign will be presented in individual data listings.

10.24.2 Minimal, Maximal and Most Extreme Value for Laboratory Measurements

The minimal value is defined as the lowest value from assessments taken during the period of interest.

The maximal value is defined as the highest value from assessments taken during the period of interest.

The most extreme (ME) value is defined as the furthest value from normal range in either direction collected during the period of interest.

Let's define for a given patient and a given parameter x:

- n: the number of observations collected during the studied period,
- i= 1, 2, 3,...,n xi the values of the study parameter for that patient during the studied period,
- LLN: the lower limit of normal range of the study parameter,
- ULN: the upper limit of normal range of the study parameter,
- ME: the most extreme value of the study parameter,
- i= 1,2, 3,...,n yi the distance of each collected laboratory value xi to the reference range
- If the parameter has only a LLN then yi= LLN-xi
- If the parameter has only a ULN then yi= xi- ULN
- If the parameter has both a LLN and a ULN then yi= max (LLN-xi, xi- ULN)

Consequently ME= xi such as yi=max (y1, y2,....y1,...yn). In case of ties, the measurement xi presenting the highest change from baseline in absolute values will be used.

10.25 Columbia Suicide Severity Rating Scale (C-SSRS)

The C-SSRS scale is composed of 11 items answered Yes or No. Ten of them are ordered in categories as described below to determine the studied endpoints.

5 subtypes of suicidal ideation

- Category 1 Wish to be Dead
- Category 2 Non-specific Active Suicidal Thoughts
- Category 3 Active Suicidal Ideation with Any Methods (Not Plan) without Intent to Act
- Category 4 Active Suicidal Ideation with Some Intent to Act, without Specific Plan
- Category 5 Active Suicidal Ideation with Specific Plan and Intent.

5 subtypes of suicidal behavior

- Category 6 Preparatory Acts or Behavior
- Category 7 Aborted Attempt
- Category 8 Interrupted Attempt,
- Category 9 Actual Attempt (non-fatal)
- Category 10 Completed Suicide.

Last item

• Self-injurious behavior without suicidal intent

The C-SSRS also includes a suicidal ideation intensity rating from 1 (least severe) to 5 (most severe).

The following composite endpoints will be assessed based on the categories described above:

- Suicidal ideation (Yes/No): is Yes if one of the categories from 1 to 5 is answered Yes
- Suicidal behavior (Yes/No): is Yes if one of the categories from 6 to 10 is answered Yes
- Suicidal ideation or behavior (Yes/ No): is Yes if one of the categories from 1 to 10 is answered Yes
- Self-injurious behavior without suicidal intent (Yes /No): is Yes if this question is answered Yes.

The following scores will be derived as follow:

- Suicidal ideation score is rated from 1 to 5 according to the most severe suicidal ideation category answered Yes and is assigned to 0 if categories 1 to 5 are answered No,
- Suicidal ideation intensity rating score (0 to 25) will be defined as the sum of the 5 features described below (ranging from 0 to 5, 0 being the least severe and 5 being the most severe) rated with respect to the most severe type of ideation category
 - Frequency
 - Duration,
 - Controllability
 - Deterrents
 - Reason for ideation.

Comparative endpoints will also be defined as described below:

Treatment emergent outcomes will include any events that first emerge or worsen whereas emergent outcomes will refer to outcome that first emerge.

- Treatment-emergent suicidal ideation compared to recent history (not using C-SSRS taken during screening):
 - Increase from baseline in suicidal ideation score.
- Treatment-emergent serious suicidal ideation compared to recent history (not using C-SSRS taken during screening):
 - Increase in suicidal ideation score from a baseline (0-3) to (4-5).
- Emergence of a serious suicidal ideation compared to recent history (not using C-SSRS taken during screening):
 - Increase in suicidal ideation score from baseline (0) to (4-5).
- Emergence of suicidal behavior compared to all prior (using C-SSRS taken at and post screening assessments):
 - Occurrence of suicidal behavior (categories 6-10) post baseline with no screening or baseline suicidal behavior.

No imputation should be done with regards to missing data.

11.0 Interim Analyses

Not applicable.

12.0 Statistical Methods

All analyses will be performed in SAS® version 9.4 or higher.

Standard summary statistics for continuous and discrete variables

Summaries will be tabulated by treatment arm and overall, unless otherwise specified.

Unless otherwise noted, categorical data will be summarized using non-missing counts and percentages. Percentage will be using with the number of patients (or the number of patients at risk) in the treatment arm and, as appropriate, in the analyzed categories as denominator.

Percentages will be rounded to one decimal place except 100% which will be displayed without any decimal places and percentages which will not be displayed for zero counts.

Ratios will be presented with 2 decimal places and adjusted proportions will follow percentage rules but could be rounded to 1 or 2 decimal places according to meaningful precision.

Continuous data will be summarized using the number of non-missing observations (n), mean, standard deviation (SD), median, first quartile (Q1), third quartile (Q3), minimum (Min), and maximum (Max).

Minimum and maximum will be rounded to the precision of the original value. Mean, median, Q1 and Q3 will be rounded to 1 decimal place greater than the precision of the original value. The SD will be rounded to 2 decimal places greater than the precision of the original value. Confidence intervals (CIs), LS means, standard error (SE), geometric mean, geometric SD and coefficient of variation (CV) (%) will be provided as appropriate. Confidence intervals, LS means and geometric mean will be presented with the same precision as the mean value whereas SE and geometric SD will be presented with the same precision as SD and the CV (%) will be presented with 1 decimal place.

Inferential statistics

P-values will be presented to 4 decimal places. P-values less than 0.0001 will be presented as "<0.0001" and p-values greater than 0.9999 will be presented as ">0.9999".

Statistical hypothesis testing will be 2-sided and carried out at the 5% level of significance. Testing will be performed on the primary endpoint and secondary endpoints as appropriate.

To control for Type 1 error, the primary endpoint and efficacy secondary endpoint will be tested hierarchically, starting with the primary endpoint, followed by the secondary endpoint. No additional adjustments for multiplicity will be made for the other secondary endpoints and for the exploratory endpoints although nominal p-values will be presented.

Individual listings.

All the listings will be displayed sorted by treatment arm, patient identifier and date of assessment. They will include age, gender, race, country and randomization strata (as needed). A flag informing whether or not the data are impacted by COVID-19 may also be added.

Back-up model selection for the mixed model of repeated measure (MMRM)

In case of non-convergence, back-up models will be used changing the method of degrees of freedom approximation, using another variance-covariance matrix or removing one or both randomization strata from the model, following the below steps until convergence is achieved.

- Step 1: Model including Unstructured (UN) covariance matrix and Kenward-Roger (KR) method of degrees of freedom approximation.
- Step 2: Replace Kenward-Roger (KR) method of degrees of freedom approximation with the Satterthwaite (SAT) approximation.
- Step 3: Repeat Steps 1 and 2 using the following covariance structures, instead of unstructured, in the order described below
 - 1. Toeplitz (TOEP)
 - 2. First order autoregressive (AR(1))
 - 3. Compound symmetry (CS)
- Step 4: If convergence has still not been achieved, repeat Steps 1-3 including only the randomization strata of region.
- Step 5: If convergence has still not been achieved, repeat Steps 1-3 including only the randomization strata of prior cannabis use.
- Step 6: If convergence has still not been achieved, repeat Steps 1-3 with no randomization strata included.

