# 13.1 Sample Size, Power, and Significance Levels

446 patients will be randomized to the nabiximols or placebo treatment arms on a 1:1 basis.

The following assumptions have been used for the sample size:

- Common standard deviation of 6.5 for the change from baseline in average daily spasm count for nabiximols and placebo treatment arms
- True mean difference of -2 between the mean change from baseline in average daily spasm count in the nabiximols treatment arm compared to the placebo treatment arm

Using the above assumptions, the total sample size of 446 patients (223 patients per treatment arm) will have 90% power to detect a difference between treatment arms in change from baseline in average spasm count of -2 using a 2-sided hypothesis test at the 5% significance level.

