# 13.6.1 Primary Endpoint

The primary endpoint is the change from baseline in average daily spasm count (the average daily spasm count from Days 57 to 84 compared to the average daily spasm count for the baseline period) for all randomized patients regardless of treatment compliance.

The average daily spasm count will be calculated for the baseline period and each 28-day period corresponding to Days 1 to 28, Days 29 to 56, and Days 57 to 84. The change from baseline for average daily spasm count will be calculated for Days 1 to 28, Days 29 to 56, and Days 57 to 84.

Average daily spasm count for each period is defined as follows:

Total spasm count for the period Number of days in which the daily diary was completed during the period

For post-randomization data, the average daily spasm count over the 28-day period will only be calculated if there are  $\geq 15$  days of non-missing data and < 10 consecutive days of missing data. If there are < 15 days of non-missing data or  $\geq 10$  consecutive days of missing data then the average daily spasm count for the 28-day period will be set to missing.

The average daily spasm count and change from baseline will be summarized by treatment for each 28-day period.

The change from baseline will be analyzed using mixed model repeated measures (MMRM), using data for each 28-day period. The model will include baseline average daily spasm count, prior cannabis use, region (US versus non-US), period, treatment arm,

period by treatment arm interaction, and period by baseline interaction as fixed effects. Period repeated within each patient will be included as a repeated effect. Denominator degrees of freedom adjustment will be performed using the Kenward-Roger method.

The within-patient correlation structure will be modelled using an unstructured covariance matrix. If the model does not converge the following structures will be used in order of preference Toeplitz, first-order autoregressive and Compound symmetry.

The least squares mean estimates for each treatment arm and period, along with the standard error and 95% confidence intervals (CIs), will be presented. In addition, estimates of the treatment difference at each period in change from baseline will be presented along with standard errors of the difference and 95% CIs. The primary comparison is the estimate of the treatment difference for the Days 57 to 84 period.

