8.2 Sample Size Considerations

A total of 446 patients are planned to be randomized to the nabiximols or placebo treatment arms on a 1:1 basis.

The following assumptions have been used for the sample size:

- Common standard deviation of 6.5 for the change from baseline in average daily spasm count for nabiximols and placebo treatment arms
- True mean difference of −2 between the mean change from baseline in average daily spasm count in the nabiximols treatment arm compared to the placebo treatment arm

Using the above assumptions, the total sample size of 446 patients (223 patients per treatment arm) will have 90% power to detect a difference between treatment arms in change from baseline in average spasm count of -2 using a 2-sided hypothesis test at the 5% significance level.

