12.5.2.1 Primary Efficacy Analysis

The primary analysis on the primary estimand (see Section 9.1) will be analyzed using mixed model repeated measures (MMRM) performed with the SAS® MIXED procedure. The comparison between nabiximols and placebo will be performed at a type I error level of 0.05 (two-sided).

This model will include the baseline average daily spasm count and all the available post baseline average daily spam counts (as described in Section 9.1) from all patients from the FAS.

The preferred model will include the fixed categorical effects of treatment arm, timepoint, randomization strata of prior cannabis use, randomization strata of region, treatment arm-by-timepoint interaction, as well as continuous fixed covariates of baseline average daily spasm count, and baseline-by-timepoint. The timepoint effect repeated within each patient will be included as a repeated effect.

An unstructured matrix will be used to model the within-patient error variance-covariance. The denominator degrees of freedom will be calculated according to Kenward-Roger method.

The timepoint effect will have 3 levels: Week 1 to 4, Week 5 to 8 and Week 9 to 12.

Stratification classification will be obtained from the 'Randomization eCRF' page as this will show the true classification in case of mis-stratification.

This model will provide at each time point (Week 1 to 4, Week 5 to 8, Week 9 to 12), the least squares (LS) mean estimates for each treatment arm, along with the standard errors and 95% confidence intervals (CIs)

as well as, the LS mean estimates of the treatment difference in change from baseline in average daily spasm count along with standard errors of the difference and 95% CIs. T-statistics corresponding to the Type III sum of squares for difference in least square means will be used to obtain the p-value for the treatment arm comparison at Week 9 to 12 (primary timepoint).

In case of non-convergence of the preferred model or memory space issue a back-up model will be as mentioned in Section 12.0.

Additionally, LS means change from baseline and 95% CI will be plotted by Week per treatment arm.

Model assumption assessment

Distribution of the residuals will be assessed, based on outcome of the primary efficacy endpoint as follow:

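### If the unstructured fit fails, every back-up covariance structure assumes equal variance across periods, so the Week 9–12 standard error is right only if that assumption holds

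*SAP*

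**What the plan says.** SAP 12.5.2.1 specifies an MMRM with three timepoints (Weeks 1–4, 5–8 and 9–12), an unstructured within-patient matrix and Kenward-Roger degrees of freedom. Baseline and baseline-by-timepoint are covariates. The primary p-value is the treatment comparison at Week 9–12. On failure, "In case of non-convergence of the preferred model or memory space issue a back-up model will be as mentioned in Section 12.0".

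The sequence in SAP 12.0 is:

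- Step 2 keeps the unstructured matrix and replaces Kenward-Roger with Satterthwaite.
- Step 3 reads "Repeat Steps 1 and 2 using the following covariance structures, instead of unstructured, in the order described below", followed by TOEP, AR(1) and CS.
- Steps 4 to 6 repeat Steps 1 to 3 with one or both randomization strata removed.

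Protocol 13.6.1 has the same list: "If the model does not converge the following structures will be used in order of preference Toeplitz, first-order autoregressive and Compound symmetry". Neither document mentions a heterogeneous-variance structure or an empirical (sandwich) standard error.

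SAP 12.5.3.1 applies the same approach to the MSSS-88 total score, with two timepoints (Weeks 8 and 12). The SAP addendum keeps the inferential analyses of these two endpoints, drops their sensitivity and supplemental analyses, and reduces the exploratory efficacy endpoints to listings.

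**The concern.** An unstructured matrix gives each period its own variance. TOEP, AR(1) and CS differ in how correlation changes with lag, but each has one variance parameter. If the true residual variances differ, the model-based standard error at Week 9–12 uses a compromise over the three periods. Kenward-Roger and Satterthwaite do not correct a misspecified covariance. Step 2 changes only the degrees of freedom, so it would not by itself cure a REML convergence failure. In practice the sequence goes from unstructured to an equal-variance model, before an unstructured matrix with a stratum removed is tried.

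Unequal variances are plausible because the model conditions on baseline. If correlation with baseline decays over time, residual variance grows, and Week 9–12 is the period furthest from baseline. The pooled standard error would then be too small there. If variance fell, it would be too large and power would be lost. At stake are the p-value and 95% CI for the primary endpoint, in the rare case that the fallback is used. After early termination no planned sensitivity analysis would show the problem.

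**Working it through.** **1. The plan's own figure.** Inputs from SAP 8.2 and Protocol 13.1: difference −2, two-sided alpha 0.05, power 90%, and "Common standard deviation of 6.5 for the change from baseline in average daily spasm count for nabiximols and placebo treatment arms".

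n per arm = 2(1.960 + 1.282)² × 6.5² / 2² ≈ 222. At 223 per arm, power is 90.1% (normal) or 90.0% (t). The stated 446 patients and 90% reproduce. This is the only SD given; there is none by period.

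**2. Standard error under a fallback.** With complete data and a model saturated in treatment by period, the Week 9–12 estimate does not depend on the covariance structure. Only its standard error does. To a close approximation:

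- r = fallback SE / correct SE = √[(SD₁² + SD₂² + SD₃²)/3] / SD₃
- two-sided type I error = 2[1 − Φ(1.96 r)]

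Example with assumed SDs 5.2, 5.85, 6.5: mean variance = (27.04 + 34.22 + 42.25)/3 = 34.50; r = 5.874/6.5 = 0.904; 1.96 × 0.904 = 1.77; error 7.7%.

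**3. Assumed period SDs, with 6.5 at Week 9–12.** The simulated column comes from 4000 null trials per scenario with N = 446, the SAP fixed effects, REML, assumed correlations 0.8 and 0.7, and 0% or 15% dropout by Week 12. It used a t reference with N − 8 df in place of Kenward-Roger. Monte Carlo SE is about 0.35 to 0.5 points.

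| SDs by period | r | Type I error, formula | Simulated, TOEP/AR(1)/CS |
|---|---|---|---|
| 6.5 / 6.5 / 6.5 | 1.000 | 5.0% | 5.0–5.1% |
| 5.85 / 6.2 / 6.5 | 0.952 | 6.2% | 5.9–6.3% |
| 5.2 / 5.85 / 6.5 | 0.904 | 7.7% | 7.9–8.3% |
| 4.5 / 5.5 / 6.5 | 0.855 | 9.4% | 8.8–10.2% |
| 7.5 / 7.0 / 6.5 | 1.079 | 3.4–3.5% | 3.4–4.0% |

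The unstructured fit gave 4.6–5.6% throughout. For 4.5 / 5.5 / 6.5 without dropout, the mean fallback SE was 0.53 against an actual 0.63. With SDs 7.5 / 7.0 / 6.5, power falls to about 87%. At N = 80 (SDs 5.2 / 5.85 / 6.5, 10% dropout) the fallbacks gave about 7.6% and the unstructured fit 5.3%, so the error is not a small-sample effect.

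**4. A mechanism for rising variance.** Assume raw 28-day averages follow a stationary AR(1) process with adjacent-period correlation ρ. Given baseline, the period variances are proportional to 1 − ρ², 1 − ρ⁴ and 1 − ρ⁶; for ρ = 0.8 these are 0.36, 0.59 and 0.74. Fitting TOEP or AR(1) by likelihood to the full 3×3 matrix gives:

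| ρ | 0.5 | 0.6 | 0.7 | 0.8 | 0.9 |
|---|---|---|---|---|---|
| r | 0.95 | 0.93 | 0.90 | 0.87 | 0.84 |
| Type I error | 6.3% | 7.0% | 7.8% | 8.8% | 9.9% |

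CS agrees to within about 0.1 point.

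**5. Heterogeneous versions.** Fitted in the same way to the matrices above, TOEPH, ARH(1) and CSH give 4.8–5.6%, including when variance falls. The small departures from 5% arise where the correlation pattern is misspecified. These versions were fitted analytically and not simulated.

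**6. Covariance parameters.**

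| Structure | Three periods | Two visits |
|---|---|---|
| Unstructured | 6 | 3 |
| TOEP | 3 | 2 |
| AR(1), CS | 2 | 2 |
| TOEPH | 5 | 3 |
| ARH(1), CSH | 4 | 3 |

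With two visits the three homogeneous structures are one model, and the three heterogeneous ones are the unstructured matrix reparameterised.

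**The case against.** The strongest reply is that the fallback will almost never be used. An unstructured matrix for three periods has six parameters, and for two visits three. If it failed in 1% of trials (an assumption), a conditional error of 6–10% would add about 0.01 to 0.05 points to the overall rate; at 5% failure, at most 0.25 points. This stands, and it decides the severity. Enrolment stopped short of 446, so convergence is somewhat less certain at the final, unstated N, but that does not make failure likely.

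The second reply is that the direction is assumed. If raw averages are exchangeable (a random intercept with correlation 0.7), baseline-adjusted variances are equal and the error is exactly 5.0%. A random intercept plus AR(1) gives 6.0–8.2%, less than pure AR(1) at a similar correlation. Variance could also fall, since the mean of a count may decline on study. This stands too: the documents support a conditional range of about 3.4–10%, which includes no effect.

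A reader might also argue that titration in the first 14 days makes variance rise. For type I error that is weak: if the drug has no effect in any patient, titration creates no drug-driven spread. Only distance from baseline remains as a reason.

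Finally, unequal variances would be visible, because the addendum keeps the period-by-arm summaries, which include SDs. That would reveal the problem but would not change the prespecified standard error.

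**Conclusion.** The structural point holds: every prespecified back-up covariance structure assumes equal variance across periods, so a fallback gives the wrong Week 9–12 standard error unless the variances are equal. Given that the unstructured fit fails, two-sided type I error is about 6–10% if the Week 1–4 SD is roughly 8% to 35% below the Week 9–12 SD, 5% if the SDs are equal, and about 3.4% with SDs 7.5, 7.0 and 6.5. The period SDs are assumptions.

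A reader might infer that the trial's primary test runs at 6–10%. The documents do not support that: the figure is conditional on an unlikely failure and on variance rising with time. A reader might also infer that heterogeneous structures cure both endpoints. They do so only for the three-period model; for MSSS-88 they would refit the model that had just failed.

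Severity is minor: a refinement to consider.

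**What to change.** In SAP 12.0 Step 3, for the three-period spasm-count model, place TOEPH, ARH(1) and CSH ahead of TOEP, AR(1) and CS. If a homogeneous structure is the only one that converges, report the empirical (sandwich) standard error and name its degrees-of-freedom method, for example between-within. Use the same empirical standard error for any fallback in the two-visit MSSS-88 model.

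Protocol 13.6.1 prespecifies the homogeneous list and SAP 6.2 currently records no change from protocol, so enter the departure in SAP 6.2. Make the change before unblinding.

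The cost is wording in two SAP sections and two more variance parameters in a rarely used fallback. TOEPH saves only one parameter against unstructured, so ARH(1) and CSH are the more useful simplifications. A sandwich standard error is somewhat less stable at small N.
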